5.1.8. Exploratory Safety Endpoints

Other safety endpoints in the study are:

- The proportion of patients taking rescue medication, number of days on rescue medication, and weekly average usage of rescue medication
- The percent of patients using standard-of-care analgesic medication from week 16 to week 52
- Time to JR decision
- Survey of Autonomic Symptoms Scores:
 - number of patients reporting health symptoms for each symptom/health problem assessed at each scheduled visit
 - number of symptoms reported and total symptom impact score at each scheduled visit
- Time to AA, time to DA

The exploratory safety variables comparing incidence rate of each fasinumab dose group and placebo will be analyzed using the same method as the primary safety endpoints.

The exploratory safety variables comparing change from baseline scores of each fasinumab dose group and placebo will be analyzed using the same method as the primary safety endpoints.

Time to event endpoints will be analyzed using Kaplan-Meier approach and Cox regression will be used for comparing each fasinumab dose group and placebo by obtaining hazard ratios and their confidence intervals. The Cox regression model will include the fixed categorical effects of treatment-as-received and randomization strata.

Additionally, sensitivity analysis of the primary endpoint of incidence of destructive arthropathy as well as incidence of DA and JRs will be analyzed excluding patients who used NSAID during the trial.

Rescue Medication

The percentage of patients who use rescue medication between baseline and week 16 will be summarized by the treatment group for FAS-LTS.

Number of days patients used rescue medication during the treatment period (Day1 to Week 2, Week 2 to Week 4, Week 4 to Week 8, Week 8 to Week 12, Week 12 to Week 16...) will be summarized descriptively by treatment group. Weekly average amount of rescue medication use will be summarized by treatment group.

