#### **5.3.2. Study Drug Discontinuation**

Study drug may be permanently or temporarily discontinued due to medical need, as determined by the investigator, medical monitor, or the sponsor and according to the study stopping rules (Section 3.1.1).

Patients who permanently discontinue from study drug will be asked to remain in the study and to return to the clinic for all remaining study visits, per the visit schedule. Once patients discontinue from study drug, they can restart standard-of-care medications for the treatment of their OA pain with the exception of NSAIDs. Non-steroidal anti-inflammatory drugs can be restarted for OA pain 16 weeks after the last dose of study drug.

Patients who opt to withdraw from the study will be asked to complete the early termination visit per Section 6.2.10.

Patients who discontinue from study drug early due to a clinically relevant joint event (see Section 7.6.1.1) should return to the clinic for all remaining study visits per the visit schedule.

In the event that a patient must undergo JR surgery during the treatment or follow-up periods, they will be discontinued from study drug and asked to return to the study site for a pre-operative visit and for follow-up safety evaluations (as described in Section 6.3.4.10) 4 and 20 weeks after surgery. Pre-operative imaging (X-ray and MRI) will be obtained and submitted to the independent adjudication committee for review to ensure that an AA event is not in occurrence. Instructions for the submission process are provided in the study manual.

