##### **5.3.2.1. Reasons for Permanent Discontinuation of Study Drug**

Study drug dosing will be permanently stopped in the event of:

- A patient being randomized under amendment 3 or a subsequent amendment and treated with the 3 mg Q4W or 6 mg Q8W dosing regimen
- A patient being randomized under an earlier version of the protocol before amendment 3 and treated with the 6 mg Q4W, 9 mg Q4W, or placebo Q4W dosing regimen
- A subject developing clinically significant sensory and motor neurologic events confirmed by a neurologist's examination and graded by the neurologist as at least

moderate peripheral neuropathy limiting activities of daily living, ie, grade  $\geq 2$  according to v.4 (CTCAE); study sites should use CTCAE v.4 criteria throughout the study for consistency

- Evidence of pregnancy
- A patient developing new or worsening signs and symptoms indicative of carpal tunnel syndrome
- Continued noncompliance with protocol-defined maximum NSAID use (see Section 4.3) after appropriate counseling
- Continued noncompliance with protocol-defined maximum acetaminophen/paracetamol use (with a maximum daily dose of 2500 mg in Europe and other countries where 500 mg strength tablets/capsules are available and 2600 mg in any countries outside of Europe where 325 mg strength tablets/capsules are available) after appropriate counseling
- JR Surgery
- AESI:
  - Adjudicated arthropathy, as described in Section 7.6.1.1
  - Sympathetic nervous system dysfunction, as described in Section 7.6.1.2
- Hepatotoxicity
  - Study drug should be discontinued if:
    - a) Total bilirubin (TBL)  $>2x$  ULN or international normalized ratio (INR)  $>1.5$  and
    - b) Alanine aminotransferase (ALT) or aspartate aminotransferase (AST)  $>3x$  ULN and
    - c) No other cause for a and b is readily apparent

Other causes of ALT, AST, and TBL elevations can include alcoholic hepatitis, autoimmune hepatitis, non-alcoholic hepatitis, heritable diseases (Gilbert's Syndrome), heart failure, and viral hepatitis.

Study drug may be withheld in patients who do not meet criteria for permanently discontinuing study drug, until an alternative cause for drug-induced liver injury can be determined. The patient may be re-challenged if an alternative cause for elevated liver function tests is found and the liver function tests return to baseline, but only after discussion with the sponsor.

- Systemic hypersensitivity reaction assessed as related to study medication

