#### **6.2.6. Week 20 up to Week 52**

Complete visits and assessments are outlined in the schedule of events (Table 2). Patients who discontinue study drug should complete the end of treatment visit per the schedule of events and return for the remaining study visits, if possible. If patients are not able to continue study participation, they should return for an early termination visit, per the schedule of events.

During this period, non-NSAID standard-of-care pain medications can be taken in the event of inadequate pain relief for OA pain, and limited use NSAIDs can be used for non-OA related pain

or fever, as defined in Section 5.2.2. All patients will report their use of rescue treatment and limited use NSAIDs in their diaries from week 16 through week 52.

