4.3. Prior/Concomitant Medications and Procedures, Prohibited Medication

Medications/Procedures will be recorded from the day of informed consent until the End of Follow-up Clinic Visit. Medications will be coded to the Anatomical Therapeutic Chemical (ATC) level 2 (therapeutic main group) and ATC level 4 (chemical/therapeutic subgroup), according to the latest available version of WHO Drug Dictionary (WHODD). Patients will be counted once in all ATC categories linked to the medication.

Medication/Procedure Classifications

Prior medications/procedures are defined as medications/procedures starting prior to the first dose of study drug.

Concomitant medications/procedures are defined as medications/procedures starting prior to or during each respective on-treatment period (as defined in Section 5.8) and ending during or after the respective on-treatment period.

Post treatment medications/procedures are medications/procedures starting after the on-treatment period (as defined in Section 5.8).

Prohibited Medication

Patients were required to discontinue all non-study pain medication (oral or topical; except up to 150 mg/day of aspirin/5-ASA, which is permitted for cardiac prophylaxis, per local guidelines) and opioid analgesic medications, starting at the pre-randomization phone call/visit.

Analgesic medications (including tramadol) were prohibited through week 16. Patients were directed not to take concomitant medications that contain NSAIDs (oral or topical, except up to 150 mg/day of aspirin/5-ASA, which is permitted for cardiac prophylaxis) during treatment period 1. Patients could have taken non-NSAID standard-of-care therapy in addition to study drug, in the event of inadequate pain relief for OA pain, starting after the week 16 visit. Though use of oral NSAIDs should generally be avoided, a limited use is allowed after week 16 for non-OA related pain or fever after week 16. A list of medications containing NSAIDs will be provided in the study reference manual. The dose of oral NSAIDs may be increased and topical NSAIDs may be used during the follow-up period, but no earlier than 16 weeks after the last dose of study drug.

Other excluded drugs during treatment period 1 are:

- Medical marijuana
- Hyaluronic Acid Intra-articular Injections
- Cyclobenzaprine, carisoprodol, orphenadrine, tizanidine

For efficacy sub-study only during treatment period 1:

- Glucosamine sulfate
- Chondroitin sulfate

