4.5.1. Primary Safety Variables

The primary safety endpoint in the study is safety monitoring including AE incidence, SAE, incidence, AESI incidence, changes in safety lab analyses, and incidence of anti-fasimumab antibody formation from baseline to week 52 (treatment period 1 and 2) and to week 72 (end of follow-up period).

More specifically, this includes:

- Incidence of adjudicated arthropathy events
- Incidence of destructive arthropathy events
- Incidence of JR (All JRs and AESI JRs) events – including endpoint for all JRs by the telephone survey approximately 52 weeks after the last dose of study drug
- Incidence of peripheral neurosensory AESI events

- Incidence of sympathetic nervous system dysfunction AESI events
- AE incidence, SAE incidence, changes from baseline in safety laboratory analyses, and incidence of anti-fasimumab antibody formation
- Change from baseline in minimum joint space width of the index joint (knee, hip)
- Incidence of confirmed orthostatic hypotension from baseline

The raw incidence rate is defined as the number of events divided by the duration of the observation period and presented as number of events per 100 patient-years.

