5.1.4. Prohibited Medications

Number and percentage of patients with prohibited medications will be descriptively summarized by treatment group, and combined fasinumab based on the SAF-LTS. The tables will be sorted by decreasing frequency of ATC Level 2, ATC Level 4, and preferred term in the combined fasinumab group.

The number of patients with NSAID use during treatment period 1 will be summarized by treatment group, and combined fasinumab. Additionally, the number of patients with more than the limited amount of NSAID use during treatment period 2 will be summarized by treatment group, and combined fasinumab for patients in the SAF-LTS.

Total NSAIDs-use days during each treatment period and follow-up (before AA for patients with AA) will be summarized by treatment group, and combined fasinumab for patients in the SAF-LTS. Additionally, days from last study drug dose to first NSAID dose will be summarized by treatment group, and combined fasinumab for patients in the SAF-LTS.

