5.1.6.3. Length of Study Observation

The length of the observation period (days) will be calculated as:

- $(\text{Date of last study visit [up to End of Follow-up Clinic Visit]} - \text{date of first study drug dose}) + 1.$

The length of the total study observation period (days) will be calculated as:

- $(\text{Date of last study visit [up to End of Study Phone call]} - \text{date of first study drug dose}) + 1.$

The observation duration will be summarized for each treatment group using the number of patients (n), mean, standard deviation, median, Q1, Q3, minimum, and maximum.

The number (%) of patients with observation periods will be presented by specific time periods. The time periods of interest are specified as: ≥ 1 day, ≥ 29 days, ≥ 57 days, ≥ 85 days, ≥ 113 days, ≥ 141 days, ≥ 169 days, ≥ 197 days, ≥ 225 days, ≥ 253 days, ≥ 281 days, ≥ 309 days, ≥ 337 days, ≥ 365 days, ≥ 393 days, ≥ 421 days, ≥ 505 days, ≥ 701 days

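### The supportive DA and DA/JR analysis that drops NSAID users sets no time order, so NSAID use after an event can remove the event and bias the arm rates and rate difference

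*SAP*

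**What the plan says.** SAP 5.1.8 plans a sensitivity analysis of DA incidence, and of DA and JR incidence. Both "will be analyzed excluding patients who used NSAID during the trial". No time window is given, the event date is not mentioned, and there is no censoring. SAP 5.1.7.1 asks for arm rates, rate ratio and rate difference from a Poisson model with log observation days as the offset.

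Four other provisions determine who counts as a user:

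- Protocol 5.3.2.1: "Study drug dosing will be permanently stopped in the event of" a list of conditions that includes JR surgery and adjudicated arthropathy (AA). DA is determined among AA cases (Protocol 7.6.1.1).
- Protocol 5.3.2: patients who stop drug are asked to remain in the study, and "Non-steroidal anti-inflammatory drugs can be restarted for OA pain 16 weeks after the last dose of study drug".
- SAP 4.3: "Medications/Procedures will be recorded from the day of informed consent until the End of Follow-up Clinic Visit".
- SAP 5.1.4 respects the order of exposure and event in its NSAID summary, which reports "Total NSAIDs-use days during each treatment period and follow-up (before AA for patients with AA").

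**The concern.** An event stops study drug. Stopping drug starts the 16-week clock after which NSAIDs are open for OA pain. Recording continues, so later use is captured. The exclusion therefore selects on something that can follow from the outcome. If cases become NSAID users more often than non-cases, they are removed disproportionately and the rates fall; if less often, the rates rise. Neither shift needs any effect of NSAIDs on joints.

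Protocol 1.1 and 1.2 describe more joint damage when anti-NGF drugs are combined with NSAIDs, and Protocol 1.3.1 says the study will provide safety data on concomitant use. A lower rate after exclusion could be read as showing that NSAIDs explain part of the joint events, and an unchanged rate as showing that they do not. As specified, the analysis supports neither reading.

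**Working it through.** **Plan's own figure.** None is given for this analysis. The only stated precision for safety incidence is the table of exact intervals: 52/5250 gives 0.741% to 1.297%, matching the printed 0.74% to 1.30%. It concerns incidence without any exclusion.

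**Formula.** When whole patients are removed, and non-cases carry nearly all the person-time,

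rate after exclusion ≈ true rate × k, with k = P(no NSAID use | case) / P(no NSAID use | non-case).

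The rate difference becomes k₁r₁ − k₀r₀ and the ratio (k₁/k₀)(r₁/r₀). Equal k in both arms preserves the ratio but not the rates or the difference.

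**Schedule arithmetic.** Limited NSAID use opens at week 16 and the limits lift 16 weeks after the last dose. Take a completing non-case (last dose week 48) and a case whose last dose was week 20. Assume weekly NSAID-start hazards of 0.005 under limits and 0.03 once lifted; neither is in the documents.

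| Patient | Weeks limited | Weeks unrestricted | P(no use) |
|---|---|---|---|
| Non-case, to week 72 | 16–64 = 48 | 64–72 = 8 | exp(−0.24 − 0.24) = 0.619 |
| Case, to week 72 | 16–36 = 20 | 36–72 = 36 | exp(−0.10 − 1.08) = 0.307 |
| Case, to last dose + 24 (week 44) | 16–36 = 20 | 36–44 = 8 | exp(−0.10 − 0.24) = 0.712 |

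So k = 0.307/0.619 = 0.50 under the first follow-up and 0.712/0.619 = 1.15 under the second. With one hazard of 0.005 throughout and follow-up to week 72, both have P(no use) = exp(−0.005 × 56) = 0.756 and k = 1.

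The documents support both follow-up readings. Protocol 5.3.2 and 6.2.7 ask patients off drug to attend all remaining visits; Protocol 3.1 (Follow-up Period) and 6.2.8 describe 24 weeks after the last dose.

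**Simulation over all event times.** Assumptions: true rates 2 and 4 per 100 patient-years, no NSAID effect, hazards 0.005–0.010 under limits and 0.03–0.05 once lifted, 0% or 30% of non-cases stopping early.

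| Setting | Rates after exclusion | Difference (true 2.0) |
|---|---|---|
| Followed to week 72 | 1.2–1.6 and 2.3–3.1 | 1.1–1.6 |
| Followed to last dose + 24 weeks | 2.2–2.5 and 4.3–4.9 | 2.1–2.5 |
| Week 72, equal hazards | 2.0 and 4.0 | no bias |

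In the week 72 setting 56–79% of cases but 38–66% of non-cases are excluded, and 44–59% of cases first use an NSAID only after the event. The ratio stays at about 1.9–2.1.

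**When the ratio moves.** If the unrestricted hazard is 0.05 in one arm and 0.03 in the other (week 72), the true ratio of 2 becomes 1.6–1.7 when use is higher on fasinumab and 2.3–2.4 when it is higher on placebo.

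**Alternatives under the same assumptions.** Censoring events and person-time at first NSAID use gives 1.95–2.05 and 3.95–4.07. Excluding only patients whose use preceded the event gives 2.3–4.3 and 4.7–8.9: non-cases are still dropped for use at any time, while cases are dropped only for early use.

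**The case against.** **The phrase is undefined.** The SAP does not say in terms that use after the event counts, and its 5.1.4 wording suggests that the authors understood the order. That is fair. But a rule with no time limit, applied to medications recorded to End of Follow-up, includes later use on its plain reading.

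**Size and sign are assumed.** This stands. With a smaller rise in NSAID start (0.010 to 0.015 per week, week 72, no early stopping) the rates are 1.82 and 3.60, against about 1.97 and 3.90 without exclusion: roughly 8% lower. A reader might infer that the exclusion must understate joint risk; the documents do not support a fixed direction.

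**Joint replacements found by telephone.** SAP 4.5.1 lists JR incidence "including endpoint for all JRs by the telephone survey approximately 52 weeks after the last dose of study drug", while NSAID recording ends earlier, so a reader might infer that JRs between weeks 72 and 100 enter this analysis with no NSAID record. The documents point the other way. SAP Section 7 limits the extra work at week 100 to JR incidence from the telephone survey and updates for changed data. SAP 5.1.6.3 defines the observation period by "Date of last study visit [up to End of Follow-up Clinic Visit"], separately from the longer period to the phone call. Nor is the diary limit ("All patients will report their use of rescue treatment and limited use NSAIDs in their diaries from week 16 through week 52") a gap in itself, because concomitant medications continue to End of Follow-up.

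**Censoring is not always better.** Also true. If NSAID start rises fivefold in the 8 weeks before the event, unlagged censoring gives 1.6–1.8 and 3.1–3.6. With follow-up ending 24 weeks after the last dose, the exclusion gives 1.8–1.9 and 3.8–4.0 there, closer to the truth only because two opposite biases offset.

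**It is exploratory.** The objective is descriptive, and SAP 5.1.8 does not claim to estimate an NSAID effect. This limits the weight of the point but does not remove it.

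**Conclusion.** The concern holds as a possible bias in one supportive analysis. Because the exclusion can act on NSAID use that follows the event, arm rates and the rate difference can shift with no NSAID effect: downward with follow-up to week 72, upward with follow-up ending 24 weeks after the last dose, and not at all with equal ever-use in cases and non-cases. The figures above illustrate direction and plausible scale under assumed NSAID hazards; they do not estimate what this trial will show. The rate ratio is largely safe unless NSAID use by case status differs between arms, and the documents give no evidence that it does. A reader might go further and doubt the main DA and JR results, but the primary SAF-LTS analysis excludes nobody for NSAID use and is untouched. The change is worth making before lock because it is cheap and removes a bias, with medium confidence that the bias would matter in practice.

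**What to change.** In SAP 5.1.8, keep all SAF-LTS patients in this supportive analysis and censor both events and person-time (the offset) at first post-baseline NSAID use, in line with the time order already used in SAP 5.1.4. State that it covers events up to the End of Follow-up visit, as part of the week 72 analysis in SAP Section 7. Do not replace the rule by excluding only patients with pre-event use, since that biases rates upward. A lagged version is optional, as a check on NSAID use prompted by pain before diagnosis. If the whole-trial exclusion is kept, label it descriptive and report how many cases first used an NSAID after their event.

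The cost is SAP wording and one derived date, first post-baseline NSAID use, from diaries and concomitant medications. Under the assumptions above, censoring keeps 77–90% of person-time; the whole-trial exclusion keeps 33–65% of patients. Residual bias remains if pain before diagnosis prompts NSAID use, and a long lag would dilute a real NSAID effect.

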5.1.8.1. Adverse Events

The verbatim text, the preferred term, and the primary SOC will be listed in patient listings. Summaries that include frequencies and proportions of patients reporting AEs will include the preferred terms and the SOCs.

- *Pre-Treatment Adverse Events* are defined as AEs that developed or worsened during the pre-treatment period.
- *Treatment-Emergent Adverse Events (TEAE)* are defined as those that are not present at baseline or represent the exacerbation of a pre-existing condition during the on-treatment period.
- *Post-Treatment Adverse Events* are defined as AEs that developed or worsened more than 28 days after the last dose of study drug.

The focus of adverse event reporting in the clinical study report will be on TEAEs. Post-treatment AEs and AEs during the study will be summarized similarly as TEAEs.

Summaries of TEAEs by treatment group will include:

- Overview of TEAEs, summarizing number of events, summarizing number and percentage of patients within the specified category
 - Total number of TEAEs
 - Total number of Serious TEAEs
 - Patients with any TEAEs
 - Patients with any Serious TEAEs
 - Patients with any TEAEs leading to death

- Patients with any TEAEs leading to withdrawal from study
- Patients with any TEAEs leading to permanent study treatment discontinuation
- All TEAEs by SOC and PT
- All TEAEs by SOC, PT, severity
- Study drug related TEAEs by SOC and PT
- TEAEs resulting in Permanent Study Drug Discontinuation by SOC and PT
- AESI by SOC and PT
- Serious TEAEs by SOC and PT
- Non-serious TEAEs by SOC and PT

Listing to include:

- Listing of AEs leading to death
- Listing of TEAEs leading to permanent study treatment discontinuation
- Listing of TEAEs leading to withdrawal from study
- Listing of Patients with Serious TEAEs
- Listing of Patients with AESIs
- Listing of all Joint Replacements

Counts will be provided according to treatment group and combined fasinumab group for each PT within each primary SOC. Percentages will be calculated based on the SAF-LTS in each treatment group.

Primary SOCs will be sorted by decreasing frequency in the combined fasinumab group. Within each primary SOC, PTs will be sorted by decreasing frequency in the combined fasinumab group. For tables presenting severity of events, the worst severity will be chosen for patients with multiple instances of the same event.

A second type of table with counts of each primary SOC in decreasing order of frequency will be provided. A third type of table with counts of each PT in decreasing order of frequency will also be provided. TEAEs with preferred terms $\geq 5\%$ in any treatment group will be summarized in the report.

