## 5. STUDY TREATMENTS

### 5.1. Investigational and Reference Treatments

Under amendment 8 and amendment 9, patients will be enrolled into the main safety study and randomized to 1 of the following treatment arms:

- Fasinumab 1 mg SC Q8W (patients will receive placebo injections at the study visits where fasinumab is not administered)
- Fasinumab 1 mg SC Q4W
- Placebo SC Q4W

Prior to amendment 7 (urgent safety measure), patients were randomized to 6 mg Q8W or placebo in the main study (after amendment 3), and to the following treatment arms in the efficacy sub-study (amendment 5):

- Fasinumab 1 mg SC Q8W (included in the efficacy sub-study only; patients will receive placebo injections at the study visits where fasinumab is not administered)
- Fasinumab 1 mg SC Q4W
- Fasinumab 3 mg SC Q4W
- Fasinumab 6 mg SC Q8W (patients will receive placebo injections at the study visits where fasinumab is not administered)
- Placebo SC Q4W

Enrollment into the efficacy sub-study was completed prior to amendment 7.

All patients previously enrolled into the main study had completed treatment prior to amendment 7. Under amendment 7, patients randomized to 3 mg Q4W or 6 mg Q8W in the efficacy sub-study were discontinued from study drug for the remainder of the study. All patients who were discontinued from study drug immediately entered the follow-up period.

Patients originally randomized to earlier versions of the protocol (prior to amendment 3) with 9 mg Q4W, 6 mg Q4W, or placebo Q4W were discontinued from study drug for the remainder of the study under an amendment 4EU (issued on 12 January 2017) and amendment 5 global (issued on 16 March 2017).

All patients will receive SC injections Q4W from day 1 up to week 48. All SC injections will be in the abdomen, thigh, or upper arm. Study drug (fasinumab or placebo) will be administered at the study site after all study visit procedures have been completed. Patients will be observed in the clinic for approximately 1 hour after study drug is administered.

Instructions for study drug administration are provided in the pharmacy manual.

Doses of study drug must be given within  $\pm 7$  days from the scheduled dose date. If the window is missed, the dose should not be administered. The next dose should be administered at the next scheduled dosing date.

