### 9.5.3. Safety Analysis

The incidence rate is defined as the number of events divided by the duration of the overall observation period. The incidence rate will be summarized by treatment group along with 2-sided 95% confidence interval. The incidence rate differences and ratios between each fasinumab dose group and placebo will be computed and presented along with 2-sided 95% confidence intervals.

Change from baseline in joint space width of the index knee or hip will be summarized by treatment group. Time to event endpoints, such as time to JR decision, will be analyzed using the Kaplan-Meier approach.

For safety variables, the following observation periods are defined:

- The pretreatment period is defined as the time from signing the ICF to before the first dose of study drug
- The on-treatment period is defined as the day of the first dose of study drug to 4 weeks after the day of the last dose of SC study drug.
- The follow-up period is defined as from the end of the on-treatment period up to 24 weeks post the last dose of study drug (week 72).

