5.1.7.1. Primary Safety Endpoints

Incidence rate ratio estimates and 2-sided 95% confidence interval will be computed using Generalized Estimating Equations with a log-linked Poisson model via the PROC GENMOD procedure if there are events in the placebo group. The model will specify the use of a Poisson probability distribution with an offset= log (patient-observation period days) and model terms for treatment-as-received and each randomization strata. The 95% confidence interval for the

estimates of the difference in incidence rates will be computed using the same model. If there is no event in the placebo group, incidence rate ratio will not be calculated and confidence intervals for the incidence rate difference will be computed using Wald method. The incidence rate estimates for each arm, the estimates of the incidence rate ratio and incidence rate difference between fasinumab and placebo will be provided with the corresponding 95% confidence interval.

AE and SAE incidence will be summarized by treatment group based on the SAF-LTS by treatment group and combined fasinumab group.

Continuous variables will be summarized by baseline and change from baseline to each scheduled assessment time with descriptive statistics based on the SAF-LTS by treatment group and combined fasinumab group.

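### TEAE and serious TEAE tables give crude percentages over an on-treatment window that amendment 7 shortened in two sub-study arms but not in the placebo and 1 mg arms randomised alongside them

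*SAP*

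**What the plan says.** SAP 4.5.1 lists among the primary safety variables "AE incidence, SAE incidence, changes from baseline in safety laboratory analyses, and incidence of anti-fasimumab antibody formation". The same section gives a person-time definition: "The raw incidence rate is defined as the number of events divided by the duration of the observation period", scaled to 100 patient-years. Protocol 9.5.3 has the same definition and adds: "The incidence rate differences and ratios between each fasinumab dose group and placebo will be computed and presented".

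SAP 5.1.7.1 turns this into a model: "The model will specify the use of a Poisson probability distribution with an offset= log (patient-observation period days". A separate paragraph then deals with adverse events: "AE and SAE incidence will be summarized by treatment group based on the SAF-LTS by treatment group and combined fasinumab group". It does not say whether the rate model applies to them.

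SAP 5.1.8.1 specifies the tables as event totals plus counts and percentages of patients, by system organ class and preferred term. On the denominator it says: "Percentages will be calculated based on the SAF-LTS in each treatment group". The report is to focus on TEAEs, and SAP 5.1.7 closes the on-treatment period 28 days after the last dose. Post-treatment and whole-study AEs are tabulated in the same way. No listed AE output is per patient-year.

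On dosing, protocol 5.1 says: "Under amendment 7, patients randomized to 3 mg Q4W or 6 mg Q8W in the efficacy sub-study were discontinued from study drug". It adds that main-study patients enrolled before then had already finished treatment, and that stopped patients went straight into follow-up. Protocol 5.5 says nobody entered the main study under amendments 5 or 6, so the 3 mg Q4W arm exists only in the sub-study.

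**The concern.** A crude percentage compares arms fairly only if patients in each arm had similar time in which to have the event. Here the sponsor shortened that time in two active arms and left it alone in the placebo and 1 mg arms randomised with them. A patient whose window closes early has less chance of a recorded TEAE, so the percentage falls even when the underlying rate is the same or higher.

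This matters because arthralgia and peripheral oedema were among the imbalances that led the DMC to recommend stopping these doses (protocol 1.1 and 1.3.2). They are common preferred terms, read mainly from the TEAE tables rather than from the adjudicated-event models. A real excess at 3 mg Q4W or sub-study 6 mg Q8W could look smaller, or vanish, in the tables that give the safety context for the 1 mg regimens.

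**Working it through.** **The plan's own figure.** SAP Table 1 gives an exact 95% interval for crude incidence n/N. With 52 events in 5250 (0.99%) the Clopper-Pearson interval is 0.74% to 1.30%, as stated. That figure is correct, but it takes no account of time at risk.

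**Inputs from the documents.** Amendment 5 global issued 16 March 2017 and sub-study enrolment complete 7 February 2018 (SAP 1.1); amendment 7 issued 24 May 2018 (protocol 1.3.2); injections every 28 days from day 1 to week 48; window ending at last dose + 28 days, so a full course gives 48 × 7 + 28 = 364 days.

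**Assumptions.** Entry uniform between the two enrolment dates, stop on 24 May 2018, every dose given on schedule, no other discontinuation, constant hazard, and 10% 364-day incidence on placebo.

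**Window in the stopped arms.** Time from entry to stop runs from 106 to 434 days, a span of 328. With k = floor(days/28), the window is 28(k + 1), capped at 364.
- 106-112 days: window 112, for 6 of the 328 days
- eight 28-day bands: windows 140, 168, ..., 336, summing to 1904
- 336-434 days: window 364, for 98 of the 328 days

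Mean = (6 × 112 + 28 × 1904 + 98 × 364) / 328 = 89,656 / 328 = 273 days (39 weeks), against 364. The share cut short is 230/328 = 70%.

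**Crude risk ratio.** Cumulative placebo hazard is -ln(0.9) = 0.10536. Crude risk in a stopped arm is the average of 1 - exp(-0.10536 × HR × window/364) over those windows.

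| True HR | Stopped arm, crude | Crude ratio to 10% | Ratio with full window |
|---|---|---|---|
| 1.0 | 7.6% | 0.76 | 1.00 |
| 1.25 | 9.4% | 0.94 | 1.23 |
| 1.5 | 11.1% | 1.11 | 1.46 |

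With entry starting on 1 July 2017, or a stop on 30 April 2018, or both, the mean window ranges over 30-39 weeks and the equal-hazard ratio over 0.58-0.76.

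**Front-loaded events.** Place a share f of the cumulative hazard in the first 112 days and spread the rest evenly to day 364. For HR 1.25 the crude ratio is about 1.02 at f = 50% and 1.11 at f = 70%, so there is no reversal.

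**Would the existing offset repair it?** Not for TEAEs. If observation ends 24 weeks after the last dose, its mean is 273 - 28 + 168 = 413 days (59 weeks) in the stopped arms, against 504 (72 weeks). On-treatment time is 273/413 = 0.66 of observation in the stopped arms and 364/504 = 0.72 in full-course arms. TEAE counts divided by observation days would still give a ratio of about 0.66/0.72 = 0.92 at equal hazard.

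**Would on-treatment patient-years repair it?** Under constant hazard, yes. Placebo gives 0.10536 × 365.25/364 × 100 = 10.6 per 100 patient-years. A stopped arm gives 10.6, 13.2 or 15.9 for HR 1.0, 1.25 or 1.5, whatever the window.

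**Pooled columns.** Cohort sizes are not in the documents. Assume 200-1000 patients before amendment 3 (both arms cut, windows of 28 or 40 weeks), 1000-2000 under amendments 3/4, 1000 in the sub-study and 1000-3000 under amendment 8, with equal hazards and the planned ratios. Example with 200 (28 weeks, risk 5.5%), 1000, 1000 and 1000:
- Combined fasinumab: (160 × 5.5% + 667 × 10% + 400 × 7.6% + 400 × 10% + 857 × 10%) / 2484 = 9.3%
- Placebo: (40 × 5.5% + 333 × 10% + 200 × 10% + 143 × 10%) / 716 = 9.75%
- Ratio: about 0.96

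Across all the assumed sizes the ratio is 0.95-0.98. Pooled 6 mg Q8W shows 9.4-9.7% against 10%.

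**The case against.** **The plan already uses person-time.** It does for joint replacement, adjudicated arthropathy and the other special-interest events, through the Poisson model and the Kaplan-Meier and Cox analyses in SAP 5.1.8. Joint replacement timing was among the DMC's stated concerns. SAP 4.5.1 also defines a rate per 100 patient-years in the section that lists AE and SAE incidence. So it would be wrong to infer that the plan ignores exposure. What stands is that SAP 5.1.7.1 leaves it unclear whether rates reach AEs and SAEs, and SAP 5.1.8.1 lists none.

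**The protocol asks for percentages.** Protocol 9.5.3.1 does prescribe number and percentage for TEAEs, and the SAP follows it. That supports keeping the percentages as description. It does not make them a fair basis for comparing arms.

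**Unequal exposure will be visible.** Exposure, time to treatment discontinuation and whole-study AE tables are planned. A careful reader will see the shortfall but cannot correct each preferred term for it. The whole-study tables help only in part, because stopped patients entered follow-up early.

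**The stopped doses are gone and the objective is descriptive.** True, and amendment 7 does not cut the 1 mg versus placebo contrast. That lowers the stakes. The higher doses still provide the dose context.

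**Stronger readings to avoid.** A reader might infer that every stopped dose looks too safe. The documents do not support that. Earlier main-study 6 mg Q8W patients had finished treatment, and the 6 and 9 mg Q4W cohort was stopped together with its matching placebo (SAP 1.1), so the stop itself created no difference between arms there. A reader might also infer that the combined fasinumab column is badly distorted. Its membership is not settled: SAP 2.1 limits the SAP to the 1 mg doses and placebo, while SAP 3.2 puts everyone dosed in SAF-LTS.

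**Conclusion.** The point holds for 3 mg Q4W, whose patients are all in the sub-study, and for sub-study 6 mg Q8W. Followed as written, SAP 5.1.8.1 gives TEAE and serious TEAE percentages that favour these arms over concurrent placebo. At 10% placebo incidence a true hazard ratio of 1.25 would appear as about 0.94, and 1.5 as about 1.11. These figures are illustrations: entry pattern, event rate, constant hazard and absence of other dropout are assumptions, and front-loaded events would shrink the effect.

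The distortion is small for pooled 6 mg Q8W and about 2-5% for a combined column under assumed cohort sizes. AE and SAE incidence are parts of the primary safety endpoint, not the whole of it, so this does not call the full primary analysis into question. No number stated in the plan is wrong. The SAP should be changed, because the tables affected are the ones most readers will use for common adverse events.

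**What to change.** In SAP 5.1.8.1:

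- For TEAEs, serious TEAEs and TEAEs by preferred term, add the number of patients with the event per 100 patient-years of on-treatment time, counted from first dose to the earlier of first event and last dose + 28 days.
- Match the denominator to the window in the post-treatment and whole-study AE tables. Do not apply the observation-day offset of SAP 5.1.7.1 to on-treatment counts.
- Compare the stopped arms with placebo patients randomised over the same period.
- State which doses form the combined fasinumab group, and reconcile SAP 2.1 with SAP 3.2.
- Base between-arm statements on the rates, and keep counts and percentages as description.

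The cost is one extra column and modest programming, using dates already collected. The drawback is that a rate summarises fairly only if the hazard is roughly constant. For events concentrated early in treatment, Kaplan-Meier cumulative incidence at fixed weeks is an alternative.
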